### **Sample size (number of participants included)**

We calculated our sample size using G-power software. Our primary outcome is end to start facial nerve MEP ratio was derived from a previous study to be mean  $0.72 \pm 0.43$  calculated by using previous results (12) with SPSS program. We assumed that ratio will decrease 50%. Considering a study power of 80% and a p-value of 0.05 to be significant, the sample size was calculated to be 38 patients (19 in each group). To compensate for drop-out we will recruit 20 patients in each group.

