**Possible Risk (mention if there is any risk or not):**

No possible risk.

**Primary outcomes** (Most important outcomes to be assessed)

1- End to start facial nerve MEP amplitude ratio.

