### **Statistical analysis:**

Data will be coded and entered using the statistical package SPSS version 24. Data will be summarized using mean and standard deviation for quantitative variables and frequencies (number of cases) and relative frequencies (percentages) for categorical variables. Comparisons between groups will be done using unpaired t test when comparing 2 groups and analysis of variance (ANOVA) with multiple comparisons post hoc test when comparing more than 2 groups (13). For comparing categorical data, Chi square ( $\chi^2$ ) test will be performed. Exact test will be used instead when the expected frequency is less than 5 (14). Correlations between quantitative variables will be done using Pearson correlation coefficient (15). P-values less than 0.05 will be considered as statistically significant.

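### The 19 per group comes from a one-sided calculation; under the two-sided t test that the plan implies, power is about 71–73%, not 80%

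*Combined protocol and SAP*

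**What the plan says.** The protocol names one primary outcome: "End to start facial nerve MEP amplitude ratio". The Sample size paragraph (section 8, Study Methods) takes a mean of 0.72 and an SD of 0.43 for this ratio from a cited study and sets the effect with "We assumed that ratio will decrease 50" per cent. It then gives the error rates and the result: "Considering a study power of 80% and a p-value of 0.05 to be significant, the sample size was calculated to be 38 patients", that is, 19 per group. Recruitment is set at 20 per group to cover drop-out. The software named is G-power.

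The Statistical analysis paragraph says: "Comparisons between groups will be done using unpaired t test when comparing 2 groups". It sets one threshold for everything: "P-values less than 0.05 will be considered as statistically significant". Neither paragraph says whether the calculation or the test is one-sided or two-sided. The Objectives section speaks only of comparing two levels of muscle relaxation and does not say which group should have the lower ratio.

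**The concern.** The sample size and the analysis should rest on the same test. An unpaired t test reported against 0.05 with nothing further said is ordinarily two-sided, yet 19 per group looks too small for a two-sided test with a standardised effect of 0.837. If the calculation was run one-sided and the analysis will be two-sided, the trial does not have its stated power.

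This is the only power claim in the protocol, and it concerns the only primary outcome. If it is too high, a non-significant result may be read as adequately powered evidence that partial blockade and no blockade give similar MEP ratios, when the risk of missing the assumed effect was well above the stated 20%.

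**Working it through.** **Inputs**

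- From the Sample size paragraph: mean 0.72, SD 0.43, 50% decrease, 80% power, alpha 0.05, 19 per group calculated and 20 per group recruited.
- From the Statistical analysis paragraph: unpaired t test.
- Assumed, because not stated: the 50% is a relative decrease, and the SD is 0.43 in both groups.

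**Effect size**

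- Difference: 0.72 × 0.50 = 0.36
- Standardised effect: d = 0.36 / 0.43 = 0.837, and d² = 0.701

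**Method**

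For n per group, the t statistic has 2n − 2 degrees of freedom and noncentrality d × √(n/2). Power is the probability that this noncentral t exceeds the critical value. That value is the 95th percentile of t for a one-sided test and the 97.5th for a two-sided test (the opposite tail adds a negligible amount).

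**Reproducing the plan's figure**

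One-sided, alpha 0.05, n = 19: noncentrality 0.837 × √9.5 = 2.58, critical value 1.688 on 36 df, power 81.2%. Solving for 80% power gives n = 18.36, which rounds up to 19. This matches the protocol exactly.

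**The same inputs, two-sided**

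Solving for 80% power gives n = 23.40, so 24 per group and 48 in total.

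| n per group | noncentrality | two-sided critical t | two-sided power | one-sided power |
|---|---|---|---|---|
| 19 | 2.58 | 2.028 | 70.9% | 81.2% |
| 20 | 2.65 | 2.024 | 73.2% | 83.0% |
| 24 | 2.90 | 2.013 | 81.0% | – |

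**Cross-check by normal approximation**, n = 2(z_α + z_β)² / d²:

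- One-sided: 2 × (1.645 + 0.842)² / 0.701 = 17.6, so 18 per group
- Two-sided: 2 × (1.960 + 0.842)² / 0.701 = 22.4, so 23 per group

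**Effect detectable with 80% two-sided power, SD 0.43**

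- 19 per group: d = 0.934, difference 0.934 × 0.43 = 0.402, and 0.402 / 0.72 = 56%
- 20 per group: difference 0.391, and 0.391 / 0.72 = 54%

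**Could another reading give 19 two-sided?**

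| Reading | one-sided n per group | two-sided n per group |
|---|---|---|
| SD halves with the mean in one group (pooled SD 0.34, d = 1.06) | 12 | 16 |
| Absolute decrease of 0.5 (d = 1.16) | 10 | 13 |
| Rank test, efficiency for normal data | 20 | 25 |
| Rank test, minimum efficiency | 22 | 28 |

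None of these gives 19. Only the one-sided t test with a common SD of 0.43 does.

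**The case against.** The strongest objection is that the documents never state sidedness. An unpaired t test at 0.05 can be run one-sided, and the assumed decrease points in a direction. If a one-sided test is really intended, the arithmetic is right and power is 81.2% with 19 per group and 83.0% with 20. It stands that the two-sided reading is an inference. But the decrease enters as an effect size, with no group named as the lower one. The objective is only to compare, and the same unqualified threshold governs every comparison and correlation in the analysis. A one-sided primary test would have to be declared and justified, and it is not.

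A second objection concerns the SD. If it halved along with the mean, two-sided power would be 88.8% with 19 per group and 90.4% with 20, above the stated 80%. Smaller departures matter too: with 20 per group, two-sided power is 79% for an SD of 0.40 and 67% for 0.46. So 71–73% does depend on a common SD of 0.43. However, the plan does not describe a halved SD, and that reading reproduces 19 with neither a one-sided nor a two-sided test, so it cannot be what was calculated.

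A third is that the consequence is modest: a shortfall of 7 to 9 percentage points, with type I error, the estimate and its confidence interval unaffected. That is fair, and it is why a correction of wording is enough.

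**Conclusion.** The concern holds: the power statement is wrong as written. The 19 per group is a one-sided result, while the analysis described is by any ordinary reading two-sided. On that reading, power to detect a fall from 0.72 to 0.36 is 70.9% with 19 per group and 73.2% with 20, so the type II error is 29.1% or 26.8% where 20% is claimed. The drop-out allowance does not close the gap even if nobody is lost. The conclusion rests on a two-sided 0.05 test, a relative decrease of 50% and a common SD of 0.43. The last two are supported by the exact reproduction of 19, and the first by the absence of any one-sided hypothesis.

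**What to change.** Rewrite the Sample size paragraph, and add the word two-sided to the Statistical analysis paragraph. The text should:

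- state that the primary comparison is a two-sided unpaired t test at 0.05;
- name the assumptions: 0.72 falling to 0.36, SD 0.43 in both groups;
- give power as about 73% with 20 evaluable patients per group and about 71% with 19, or equivalently say that 20 per group gives 80% power for a reduction of about 54% (0.39);
- note that 80% power for a 50% reduction would need 24 evaluable per group.

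This costs a paragraph of wording and a less favourable stated power. It needs no extra enrolment and no change to trial conduct. If the investigators prefer to keep the 80% claim at 50%, they would have to enlarge the trial to 24 evaluable per group, or declare and justify a one-sided test. Either way, sidedness should be fixed before the primary comparison is made, because choosing it after seeing the data would undermine the reported p-value.

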### **Statistical analysis:**

Data will be coded and entered using the statistical package SPSS version 24. Data will be summarized using mean and standard deviation for quantitative variables and frequencies (number of cases) and relative frequencies (percentages) for categorical variables. Comparisons between groups will be done using unpaired t test when comparing 2 groups and analysis of variance (ANOVA) with multiple comparisons post hoc test when comparing more than 2 groups (13). For comparing categorical data, Chi square ( $\chi^2$ ) test will be performed. Exact test will be used instead when the expected frequency is less than 5 (14). Correlations between quantitative variables will be done using Pearson correlation coefficient (15). P-values less than 0.05 will be considered as statistically significant.

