### **Methodology in details :**

Before induction of anaesthesia and Before Rocronium administration, the baseline twitch response will be established with a neuromuscular nerve stimulator (NMT mechanosensor, GE healthcare, Helsinki, Finland) to achieve the maximum response of the adductor pollicise muscle.

The maximum electromyography amplitude of T1 before Rocronium administration will be considered to be the control response (Tc). The response of the adductor pollicise brevis muscle to TOF stimulation of the ulnar nerve will be monitored every 5 min and will be recorded every 30 min, and the infusion dose of Rocronium will be adjusted according to the target of the partial NMB group.

Anaesthesia will be induced by I.V. propofol (1.5-2 mg/kg) with fentanyl (2–4 mcg/kg) through syringe infusion pump. After induction, tracheal intubation will be facilitated with Rocronium (0.6 mg/kg).

Anaesthesia will be maintained by propofol and fentanyl infusions through the pump. Subjects will be randomly allocated into one of the two groups:

Group A (n=20): will receive Rocronium as muscle relaxant, maintain partial NMB T2/TC 0.5 or TOF count 2 (10) , Fentanyl will be infused at a dose range of 0.5–1mcg/kg/hr. to control the haemodynamic response to the surgical procedure within a 20% range of its preoperative value, and propofol will be infused at a dose range of 6–8 mg/kg/hr. to targeting Bispectral index at 40 -60.(11)

Group B (n=20): will not receive muscle relaxant, Fentanyl will be infused at a dose range of 0.5–1mcg/kg/hr. to control the haemodynamic response to the surgical procedure within a 20% range of its preoperative value, and

propofol will be infused at a dose range of 8–12 mg/kg/hr. to targeting Bispectral index at 25-35, after ending of monitoring of neurophysiology propofol dose will be dropped to 4–6 mg/kg/hr. targeting Bispectral index 40- 60.(11)

The mean arterial pressure during the surgery will be monitored every 5 min and will be recorded every 30 min and will be compared between the groups. Hypotension will be defined as a decrease in the mean arterial pressure of more than 20% of the preoperative value or below 55 mm Hg and will be treated by repeated 5 mg I.V. ephedrine bolus doses. Vasopressor infusion (norepinephrine in starting dose of 0.3 up to 2 mcg/kg/min) will be given if three or more ephedrine bolus doses is required. If bradycardia (60 beats min) developed, 0.6 mg of atropine will be administered.

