Intraoperative monitoring included continuous ECG, pulse oximetry, arterial pressure (via arterial line and non-invasive arterial pressure cuff) ,temperature to avoid hypothermia ,The monitoring of transcranial electrophysiology for surgery will be performed by recording MEP, bispectral index (Covidien, Aspect medical systems, inc, Norwood, USA ) and train of four.

TCMEP monitoring of the facial nerve will be performed using two stimulant corkscrew scalp electrodes (NIM Eclipse, Midtronic) placed at positions C3 and C4 (International 10–20 EEG electrode system) Potentials will be recorded from paired sub dermal needle electrodes placed in the orbicularis oris and oculi . intraoperative monitoring for all patient will be performed by a same operator .

TCMEP recording will begin (1) prior to skin incision as baseline amplitude before muscle relaxant be taken for intubation (2) at Dural closure and end \start amplitude ratio will be calculated.

After the end of surgery, anaesthetic drugs will be stopped The extubation criteria are as follows: TOF ratio > 0.9, BIS > 70, regular respiratory pattern, tidal volume of at least 5 ml/kg and SpO2 > 95% when the patient breathes spontaneously.

The patient will be sent to the PACU while the neurosurgeons will assess appearance of neurological dysfunction.

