#### Measurement tools

1- Duration of the surgery from skin incision till skin closure will be recorded. And duration of anaesthesia from intubation till closure of anaesthetic agent.

2- TOFr and BIS will be monitored continuously every 5 min and will be recorded at baseline, at intubation, at skin incision, 30 and 60 minutes after skin incision, every 30min and 1 hr after extubation.

3- Intraoperative mean blood pressure and heart rate will be monitored every 5 min and will recorded in all groups immediately after induction, at surgical incision and every 30 minutes till the end of procedure.

4- Total amount of intraoperative propofol, fentanyl, ephedrine and norepinephrine consumption will be recorded

5- Number of hypotensive episodes, and required doses of ephedrine and vasopressors ( norepinephrine in starting dose of 0.3 up to 2 mcg/kg/min)

6- The eye-opening time (defined as the period from the cessation of propofol-fentanyl administration to when the patient opened his/her eyes on command)

7- Facial nerve function will be evaluated pre-operatively, immediately postoperatively.

8- Ratio of end operative to start-operative FMEP amplitude will be monitored .

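### The primary end/start facial MEP ratio is compared by an unadjusted t test; adding the start amplitude, already recorded before any relaxant, as a covariate is a cheap possible gain in precision

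*Combined protocol and SAP*

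**What the plan says.** The Primary outcomes item names one outcome, "End to start facial nerve MEP amplitude ratio". Measurement tools repeats it as a quantity to be followed: "Ratio of end operative to start-operative FMEP amplitude will be monitored".

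The two components are defined in Methodology in details. The start value is taken "prior to skin incision as baseline amplitude before muscle relaxant be taken for intubation". The second recording is made "at Dural closure and end \start amplitude ratio will be calculated". The same section describes one induction for all patients ("After induction, tracheal intubation will be facilitated with Rocronium (0.6 mg/kg")) and only then sets out the regimens of Groups A and B.

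The Statistical analysis section gives a single two-group method for quantitative data: "Comparisons between groups will be done using unpaired t test when comparing 2 groups". ANOVA is kept for more than two groups, and Pearson correlation is listed as a separate item. No regression, ANCOVA or other covariate adjustment appears anywhere.

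**The concern.** Dividing the end amplitude by the start amplitude is itself one fixed form of baseline adjustment, but it need not be the efficient one. A ratio can stay negatively correlated with its own denominator: a patient whose start reading is low by chance tends to show a high ratio. In an unpaired t test that leftover dependence counts as noise. A model with start amplitude as a covariate removes it.

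The covariate is legitimate because it is measured before the relaxant and before the treatments differ. With 20 patients per group and one primary outcome, precision is limited, so a measurement already in hand should not be left unused without a reason. What is at stake is power and confidence interval width. The validity of the comparison is not in question.

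**Working it through.** **Inputs from the documents (Sample size section).** Reference ratio 0.72, SD 0.43; assumed decrease 50%, so 0.72 − 0.36 = 0.36; 80% power; significance level 0.05; 19 per group, raised to 20. The start-end correlation, the distribution of the ratio and the relative variability of start and end are not given. Those used below are assumptions, as is the 35% drop.

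**The plan's own figure.** d = 0.36/0.43 = 0.837. With the noncentral t, 19 per group gives 81.2% power one-sided and 70.9% two-sided. The stated 19 is therefore reproduced only by a one-sided test; the plan does not state sidedness. Two-sided, 20 per group gives 73.2%, and 24 per group would be needed for 80%. That is a separate point, but it shows there is little power to spare. Everything below is two-sided.

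**Analytic check, normal ratio, 20 per group.** If the ratio correlates with log(start) at r within groups, the residual variance is multiplied by 1 − r². The price is one degree of freedom (38 to 37) and chance imbalance in the covariate, which multiplies the variance by 1 + 1/(2n − 4) = 1 + 1/36. With the plan's d:

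| Analysis | Power |
|---|---|
| Unpaired t test | 73.2% |
| Model, absolute r = 0 | 72.0% |
| Model, absolute r = 0.2 | 73.8% |
| Model, absolute r = 0.3 | 76.0% |
| Model, absolute r = 0.4 | 79.2% |
| Model, absolute r = 0.5 | 83.6% |

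Break-even is at absolute r = 0.169.

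**How large r might be.** If log start and log end have equal SD and correlation ρ, the log ratio correlates with log start at r = −√((1 − ρ)/2). For ρ = 0.3, 0.5, 0.7 and 0.9 this is −0.592, −0.500, −0.387 and −0.224. The break-even r corresponds to ρ = 1 − 2 × 0.169² = 0.943.

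**Simulation, lognormal ratio, start and end equally variable on the log scale** (40,000 replicates, 20 per group, Monte Carlo SE at most 0.25 points). Power of the t test, then of the model of the ratio on group and log(start):

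| Scenario | t test | ρ = 0.3 | ρ = 0.5 | ρ = 0.7 | ρ = 0.9 | Ratio unrelated to start |
|---|---|---|---|---|---|---|
| 35% drop, constant CV | 61% | 75% | 71% | 66% | 62% | 60% |
| 50% drop, equal SD | 78% | 86% | 83% | 81% | 78% | 77% |
| 50% drop, constant CV | 95% | 99% | 98% | 96% | 95% | 94% |

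For the 35% drop, the mean 95% CI width is 0.45 with the t test. With the model it is 0.38, 0.41, 0.43 and 0.45 across the four values of ρ, and 0.46 if the ratio is unrelated to start.

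**Less favourable assumptions.** If the log SD of end is 1.5 times that of start, the 35% drop gives 61% for the t test against 65%, 61% and 60% at ρ = 0.3, 0.5 and 0.7. The largest loss found was with a normal ratio, a 35% drop and r = 0: 61.8% against 60.3%, or 1.5 points.

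**Type I error.** With identical distributions in both groups: t test 4.6–4.9%, model 4.4–4.9%. With equal means but SDs of 0.43 and 0.86: t test 7.2–7.6%, model 7.4–8.2%. Adjustment does not cure unequal spread.

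**The case against.** The strongest reply is that nothing is broken. The t test is valid, the outcome already uses the start amplitude as its denominator, and the gain rests on quantities the documents do not supply. All of that is true, and it is why this is put as an efficiency point.

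Three further limits stand:

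- The 14-point figure needs a 35% drop, which is not the plan's assumption, together with ρ = 0.3. At the plan's 50% drop the gains for ρ from 0.3 to 0.7 are about 3 to 8 points (equal SD) or 2 to 4 points (constant CV).
- The gain depends on start and end being about equally variable. With end twice as variable on the log scale it is essentially nil. Matching the ratio to 0.72, SD 0.43 also means that ρ = 0.3 implies a start-amplitude CV of about 49%, and ρ = 0.9 one of about 190%. The most favourable case thus assumes the most homogeneous start values.
- Lost end responses (ratio zero) dilute the gain. Assuming 10% and 20% zeros in the two groups, unrelated to start, the 35%-drop gain falls from 14 to about 7 points at ρ = 0.3 and from about 5 to 2 at ρ = 0.7.

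Two other points do not count against the change. The plan does not say whether the orbicularis oris, the oculi or some combination supplies the amplitude, but that gap affects the ratio just as much; the covariate is simply the log of whatever denominator is used. Under a proportional drop, the slope of the ratio on log(start) differs between groups. This can shrink the gain but does not invalidate the comparison.

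**Conclusion.** The concern holds. The plan's primary comparison is unadjusted, and a true baseline value that is already collected is not used as a covariate. The plan should be changed, but this is a missed efficiency, not an error, and confidence in the size of the gain is only moderate.

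If start and end are equally variable on the log scale, the gain is about 2 to 14 points of power at correlations of 0.3 to 0.7, and negligible at 0.9. It is small or nil if end amplitude is clearly more variable than start. Against that, about 1 point is lost if the ratio is unrelated to start amplitude. On the plan's own inputs, adjustment alone would bring 20 per group close to or above 80% two-sided power only if the ratio correlates with log(start) at about 0.4 or more in absolute value.

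**What to change.** Add one sentence to the Statistical analysis section for the primary outcome:

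> The primary comparison is the adjusted difference in mean end/start ratio, with 95% CI (two-sided 0.05), from a linear model of the ratio on group and log(start amplitude).

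The test and the estimate then come from one model, on the scale used for the sample size. The unadjusted t test and, if wished, a rank-based ANCOVA can be shown as sensitivity analyses without replacing it. The covariate must be fixed before any outcome data are seen.

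The cost is small. No new data are needed, and the model runs as a general linear model in the SPSS package already named. It uses one degree of freedom and may lose about 1 point of power. Nobody is excluded who would otherwise be analysed, because a patient with no measurable start response has no ratio either. A lost end response gives a ratio of zero and stays in the model, which would not be so with log(end) as the outcome.

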### **Source of funding** (is there any source of funds or not)

No source of fund.

